7.3 Sample Size

Previous clinical experience with samfilcon A lenses is useful to provide an adequate sample size for this investigation. Too few subjects will lead to a decrease in study power. The power of a study indicates the chance of making a Type II error (i.e. showing no statistical difference even though a difference actually exists). A study power of 100% would require an infinite number of subjects. In clinical studies it is generally acceptable to use a power as low as 80%, which is a good compromise between number of subjects and the risk of not detecting a true difference that exists. The Type I error rate (i.e. chance of finding a statistical difference that really doesn't exist) is typically set at 5% ($p=0.05$) chance.

In a previous study with similar lenses (ROC2-16-032), the standard deviation for logMAR VA was 0.069. A sample size of 15 subjects was calculated to have a study power of 80%.

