7.2 Hypotheses

The null hypothesis is that the difference in mean normalized logMAR VA between the two lens types is 0.05 or greater. The alternative hypothesis is that the difference is less than 0.05.

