7.6 Statistical Analysis

Continuous data will be summarized using descriptive statistics: n, mean, standard deviation, median, minimum and maximum. Categorical data will be presented by the total counts for each category and corresponding percentages. The data for each of the ordinal dependent measures (i.e., those assigned a clinical grade) will be analyzed using appropriate nonparametric techniques. Unless otherwise noted, paired t tests will be used to test for

differences in means for each of the parametric dependent variables. Differences at the $p \leq 0.05$ level will be considered statistically significant.

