7.6.1 Pass/Fail Criteria

There are no pass/fail criteria for the results of the clinical investigation.

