1.1 Procedure for logMAR Visual Acuity

1. Ensure the appropriate lenses are in place.
2. Instruct the subject to begin reading the chart at the top line or at a line they are confident they will read all 5 letters correctly.
3. If the subject does not read all 5 letters correctly on the first attempted line instruct the subject to read the line above that. If the subject does not read those 5 letters correctly, instruct the subject to read the previous line until all 5 letters on a line are read correctly.
4. Once the subject reads all 5 letters correctly on a line instruct them to continue reading each line on the chart until three or more of the five letters on a line are missed. Guessing should be encouraged.
5. Record the number of letters the subject reads correctly on each line.
6. If a subject re-reads a line or letters, their visual acuity score will be calculated based on their first response.
7. The total number of letters read correctly is converted into a logMAR visual acuity score. This score is obtained by assigning a value of logMAR = 0.02 to each letter. The top row is calibrated (according to the manufacturer's instructions) to have a MAR of 2 min arc, thus if the subject reads the entire line and no more, the visual acuity is 0.30 logMAR. Each additional letter read correctly would improve the score by 0.02 log units.

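### Section 7.2 sets a 0.05 margin hypothesis for visual acuity, but 7.6 plans only tests of difference and 7.3 explains the error rates for a null of no difference

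*Combined protocol and SAP*

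**What the plan says.** Section 7.2 states a margin hypothesis: "The null hypothesis is that the difference in mean normalized logMAR VA between the two lens types is 0.05 or greater". The alternative is a difference below 0.05.

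Section 7.3 explains sample size in other terms. It says "The power of a study indicates the chance of making a Type II error" and glosses that error as "showing no statistical difference even though a difference actually exists". Type I error is described as the "chance of finding a statistical difference that really" does not exist, at 5%. It gives an SD of 0.069 for logMAR VA from an earlier study and then states: "A sample size of 15 subjects was calculated to have a study power of 80" percent. It gives no target difference or sidedness, and does not say whether 0.069 describes single eyes or within-subject differences.

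Section 7.6 says "Unless otherwise noted, paired t tests will be used to test for" differences in means of the parametric variables, and the synopsis does the same. Section 7.6.1 adds: "There are no pass/fail criteria for the results of the clinical investigation". Section 7.6.3 plans no sensitivity analyses. About 30 subjects are to be enrolled (3.1), discontinued subjects are not replaced (3.2.3), and non-safety summaries use eligible completers (7.5).

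**The concern.** A paired t test against zero asks whether the lenses differ at all. Section 7.2 asks whether the difference can be shown to be below 0.05. A non-significant t test does not show that, and a significant one does not rule it out. With no comparison against 0.05 in 7.6 and no decision rule in 7.6.1, the primary hypothesis has no analysis attached to it.

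The explanation in 7.3 adds to the problem because it belongs to the test of difference. Under 7.2, the error to be held at alpha is concluding that the difference is below 0.05 when it is 0.05 or more. Section 7.3 uses the name Type I for the false finding of a difference, and treats missing a real difference as Type II. A report writer who follows 7.3 and 7.6 could take a non-significant p-value as meeting 7.2, or a significant one as failing it.

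**Working it through.** **Inputs.** Margin 0.05 (7.2); SD 0.069, 15 subjects, 80% power and 5% alpha (7.3); about 30 subjects (3.1); one letter is worth 0.02 logMAR, from "assigning a value of logMAR = 0.02 to each letter" (Appendix A, 1.1). Assumption unless stated otherwise: 0.069 is the SD of paired differences.

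**1. The plan's own figure.** n = (z_alpha + z_power)² × (SD/margin)² = (1.960 + 0.842)² × (0.069/0.05)² = 7.85 × 1.904 = 14.95, so 15. This is the normal-approximation n for a two-sided 5% test to detect 0.05. It is also the n for a one-sided 2.5% test of 7.2 with a true difference of 0. The figure reproduces and cannot show which hypothesis was sized.

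**2. The definitions side by side.**

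| Event | Under 7.2 | In 7.3 |
|---|---|---|
| True difference 0.05 or more, lenses declared alike | Type I | Type II |
| True difference 0, a difference is declared | Type II, if read as failing 7.2 | Type I |
| True difference above 0 but below 0.05, lenses declared alike | Correct conclusion | Type II |

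The first row holds only if a non-significant result is read as meeting 7.2. The reversal is confined to true differences of 0.05 or more.

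**3. How often the t test misses a true 0.05.** Noncentral t, two-sided 5%, noncentrality 0.05/(0.069/√n):

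| n | Chance of a non-significant result |
|---|---|
| 15 | 25.8% |
| 26 | 5.6% |
| 27 | 4.8% |
| 30 | 3.0% |

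**4. If 0.069 is a per-eye SD (assumption).** SD of differences = 0.069 × √(2(1 − ρ)), with n = 30:

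| Inter-eye correlation ρ | SD of differences | Chance of a non-significant result |
|---|---|---|
| 0 | 0.0976 | 22.6% |
| 0.25 | 0.0845 | 12.1% |
| 0.5 | 0.0690 | 3.0% |

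**5. The opposite direction, n = 30.** The standard error is 0.069/√30 = 0.0126. The t test is significant when the observed mean difference exceeds 2.045 × 0.0126 = 0.0258. Section 7.2 is met below 0.05 − 1.699 × 0.0126 = 0.0286 at one-sided 5%, or below 0.05 − 0.0258 = 0.0242 at one-sided 2.5%. With a true difference of one letter (0.02), 33.6% of trials are significant. By simulation with the SD estimated in each trial, about 12% are significant and also meet 7.2 at one-sided 5%, and 6.3% do so at one-sided 2.5%. The 2.5% figure is above zero, although the fixed thresholds leave no gap, because the estimated SD is sometimes smaller than 0.069.

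**6. Power of a test of 7.2.** At 30 subjects and a true difference of 0: 98.7% (one-sided 5%), 97.0% (one-sided 2.5%), 97.4% (two one-sided 5% tests).

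**The case against.** The strongest reply is that 7.3 is general explanatory text and that its error of wording changes no number. The only visual-acuity difference of 0.05 in the plan is the one in 7.2, and 15 follows from it, so the calculation may well have been made for 7.2. The sentences around the faulty one use power in its normal sense. This stands: correcting 7.3 alone would achieve little, and the defect that matters is between 7.2 and 7.6.

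Four stronger readings are tempting, and the documents do not support them.

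- *A reader might infer that the plan accepts a 20% risk of wrongly declaring the lenses alike.* The 20% is not printed. It is 1 − 0.80, it belongs to 15 subjects, and about 30 are planned. At 30, with 0.069 as the SD of paired differences, the risk is 3.0%. It exceeds 5% only at 26 evaluable subjects or fewer, in a study completed in one day.
- *That a non-significant result will be reported as success.* No section says so, though none prevents it.
- *That about a third of trials with a one-letter difference would be misreported.* A significant result there is correct, since a difference exists. In 33.6 − 12 = about 22 percentage points, 7.2 is not met either (one-sided 5%), so the two analyses do not conflict.
- *That 15 subjects or 80% is wrong.* Step 1 of the working reproduces it.

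What the reply does not answer is that 7.6 and the synopsis still contain no analysis against 0.05.

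**Conclusion.** The point holds as a mismatch between hypothesis and analysis, with inconsistent error definitions in 7.3 as a secondary fault. Carried out as written, the plan does not test 7.2. The sentence on power in 7.3 is wrong in any case.

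The practical size depends on what 0.069 is. As the SD of paired differences, it leaves a small risk of false reassurance at 30 subjects (3.0%). As a per-eye SD, the risk is 22.6%, 12.1% or 3.0% for inter-eye correlations of 0, 0.25 or 0.5; the plan gives no correlation. In the other direction, the two analyses disagree in about 12% or 6% of trials at a true difference of 0.02, depending on the sidedness and alpha chosen for 7.2, which are not stated. The false-reassurance figures further assume that a non-significant result is read as meeting 7.2. The sample size itself is not in question on the paired-difference reading.

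**What to change.** - **7.6 and synopsis.** Make the primary analysis the confidence limit for the mean Test-minus-Control difference in normalized logMAR VA, compared with 0.05. State the sidedness and alpha, and whether 7.2 applies in one direction or both. Say that a non-significant paired t test will not be reported as showing a difference below 0.05.
- **7.3.** Define Type I error as concluding that the difference is below 0.05 when it is 0.05 or greater, Type II error as failing to conclude this when it is true, and power as one minus the Type II error.
- **SD and power.** Say whether 0.069 is the SD of paired differences, and restate power for about 30 subjects on the chosen test. If it is, the figures in step 6 of the working apply. If it is per-eye, recompute with a stated inter-eye correlation.
- **Alternative.** If a test of difference is what is intended, restate 7.2 as a null of no difference, and keep the statement about non-significant results.

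The cost is wording in three sections and the synopsis, and one check of the earlier study's SD. No procedures change, and no subjects are added on the paired-difference reading.

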Statistical Methods: Continuous data will be summarized using descriptive statistics: n, mean, standard deviation, median, minimum and maximum. Categorical data will be presented by the total counts for each category and corresponding percentages. The data for each of the ordinal dependent measures (i.e., those assigned a clinical grade) will be analyzed using appropriate nonparametric techniques. Unless otherwise noted, paired t tests will be used to test for differences in means for each of the parametric dependent variables. Differences at the $p < 0.05$ level are considered to be statistically significant.

Sample Size Calculations: In a previous study with similar lenses (ROC2-16-032), the standard deviation for logMAR VA was 0.069. A sample size of 15 subjects was calculated to have a study power of 80%.

Table of Contents

INVESTIGATIONAL SITE AND STUDY PERSONNEL.....	2
SYNOPSIS.....	3
1.0 INTRODUCTION	10
2.0 OBJECTIVE	10
3.0 STUDY DESIGN.....	10
3.1 Description of Study Design.....	10
3.2 Selection of Study Population.....	10
3.2.1 Eligibility	11
3.2.1.1 Inclusion Criteria	11
3.2.1.2 Exclusion Criteria	11
3.2.2 Point of Enrollment and Randomization.....	11
3.2.3 Subject Completion.....	11
3.2.4 Lost to Follow-up.....	12
3.3 Investigators.....	12
3.4 Study Duration	12
3.5 Protocol Changes and Amendments	12
4.0 STUDY MATERIALS	13
4.1 Description of the Test Article(s) (Study Lenses)	13
4.2 Description of Comparator Product(s) (Control Lenses).....	13
4.3 Instructions for Use and Administration.....	13
4.3.1 Storage Requirements	13
4.3.2 Subject Instructions.....	13
4.4 Other Study Materials	14
4.5 Packaging and Labeling	14
4.6 Accountability.....	14
4.7 Masking.....	14
4.8 Product Replacement	14
4.9 Risk Assessment	14
4.9.1 Risk Related to Subject.....	15
4.9.2 Risk Related to Data Management	15
4.10 Relevance of Clinical Investigation.....	15
5.0 STUDY METHODS.....	16
5.1 Study Visits	16

5.1.1 METHODOLOGY:	16
5.1.2 Unscheduled Visits	17
5.1.3 Missed Visits.....	17
5.1.4 Post-Study Follow-up Visit	17
5.2 Study Completion	17
5.2.1 Study Termination/Suspension	17
5.2.2 Study Termination Procedure	18
5.3 Concomitant Medications/Therapy.....	18
5.4 Protocol Deviations.....	18
6.0 ADVERSE EVENTS (AE).....	18
6.1 Adverse Event Definitions.....	18
6.1.1 Adverse Event (AE).....	18
6.1.2 Serious Adverse Event (SAE).....	19
6.1.3 Serious Adverse Ocular Event	19
6.1.4 Significant, Non-Serious Adverse Event	20

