3.0 STUDY DESIGN

3.1 Description of Study Design

Approximately 30 habitual soft contact lens wearing subjects will be enrolled in this two-hour randomized, contralateral, double-masked (subject and investigator masked), repeated measures dispensing study. All subjects will be seen for a Screening/Dispensing Visit at which informed consent will be obtained and eligibility will be assessed. If subjects satisfy all eligibility criteria and none of the exclusion criteria, subjects will be dispensed study lenses according to unique randomization schedules that will be provided to each Investigator.

There are two study lenses (one test and one control). Each subject will receive a pair of study contact lenses that will be worn for approximately 2 hours (test lens in one eye and control lens in the other eye). Subjects will complete a minimum of 1 study visit and a maximum of 2 study visits.

Visit 1: Approximately 20 minutes

Visit 2: Approximately 15 minutes

Both study visits will occur on the same day.

The clinical investigation will take approximately 2 weeks to complete.

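### Is the stated 80% power with 15 subjects wrong for the planned paired t test, and does it matter that no power is given for the roughly 30 subjects enrolled?

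*Combined protocol and SAP*

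**What the plan says.** Section 7.3 takes its variability from an earlier study of similar lenses, in which "the standard deviation for logMAR VA was 0.069". It sets out 80% as an acceptable power, says that the Type I error rate "is typically set at 5" per cent, and concludes: "A sample size of 15 subjects was calculated to have a study power of 80" per cent. The synopsis repeats the SD and the conclusion.

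The other ingredients are elsewhere. Section 7.2 gives the null hypothesis that "the difference in mean normalized logMAR VA between the two lens types is 0.05 or greater", and adds: "The alternative hypothesis is that the difference is less than 0.05". For the analysis, the synopsis and section 7.6 both say that, by default, "paired t tests will be used to test for differences in means for each of the parametric dependent variables", at the 0.05 level. Section 3.1 gives the planned size: "Approximately 30 habitual soft contact lens wearing subjects will be enrolled". Each subject wears the test lens in one eye and the control lens in the other, so the comparison is paired.

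Four inputs to the 15 are not stated: that 0.05 was the difference or margin used, whether alpha is one- or two-sided, which formula or test was used, and whether 0.069 refers to between-eye differences or to single eyes. Nothing links 15 to 30.

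**The concern.** A power statement should describe the planned test at the planned size, and on its face this one does neither. The standard calculation that returns exactly 15 and 80%, with a true difference of 0 for the margin tests, uses the normal distribution. A paired t test on 15 subjects has only 14 degrees of freedom, so the approximation flatters it by about six points (80.1% against 74.2%). The reader is also left without a power for the 30 subjects actually enrolled. Section 7.5 restricts non-safety summaries to eligible completers, and section 3.2.3 rules out replacing subjects discontinued after randomization, so the analysed number could fall below 30.

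If the shortfall were real at the size of the trial, the comparison of visual acuity could miss its aim. The type of SD adds to the worry: a single-eye SD of 0.069 could imply a larger SD for the paired difference, and lower power than the plan suggests.

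**Working it through.** **Inputs.** SD 0.069 and power 80% (section 7.3); alpha 5% (sections 7.3 and 7.6); difference or margin δ = 0.05 (section 7.2); paired design and about 30 subjects (section 3.1). Assumed, because not stated: 0.069 is the SD of the between-eye difference, and the true difference is 0 for the margin tests.

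**Reproducing the 15.** Two-sided 5% normal approximation for paired data (the same as one-sided 2.5% against the margin):

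n = ((z₀.₉₇₅ + z₀.₈₀) × SD / δ)² = ((1.960 + 0.842) × 0.069 / 0.05)² = 14.95, rounded up to 15.

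Power at 15 = Φ(0.05 × √15 / 0.069 − 1.960) = Φ(2.807 − 1.960) = 80.1%.

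So the plan's figure reproduces.

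**Exact t-test power.** This uses the noncentral t distribution with n − 1 degrees of freedom and noncentrality δ√n / SD, which is 2.807 at n = 15 and 0.05 × √30 / 0.069 = 3.969 at n = 30. The equivalence rows are the probability that both one-sided tests reject.

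| Test | n = 15 | n = 25 | n = 30 | Smallest n for 80% |
|---|---|---|---|---|
| Two-sided 5% (or one-sided 2.5% margin test) | 74.2% | 93.5% | 97.0% | 17 |
| One-sided 5% margin test | 84.7% | 97.0% | 98.7% | 14 |
| Equivalence, 5% per side | 69.3% | 93.9% | 97.4% | 18 |
| Equivalence, 2.5% per side | 49.1% | 87.0% | 93.9% | 23 |

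The column for 25 illustrates the loss of five subjects; the plan gives no dropout rate.

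**Is 15 necessarily short?** No. The alternative in section 7.2 runs in one direction, and at the plan's 5% level a one-sided t test exceeds 80% with 15 subjects. If a small true difference of 0.003 is assumed, that test has 77.9% at 14 and 80.6% at 15, so 15 is exactly the smallest adequate size. The documents state no such assumption, but they do not state the two-sided normal route either.

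**If 0.069 is a single-eye SD.** Then SD of difference = 0.069 × √(2(1 − ρ)), with ρ the between-eye correlation, which is not given:

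| Assumed ρ | SD of difference | Two-sided 5% t power at 30 |
|---|---|---|
| 0 | 0.0976 | 77.4% |
| 0.25 | 0.0845 | 87.9% |
| 0.5 | 0.0690 | 97.0% |
| 0.7 | 0.0534 | 99.9% |

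For this test, power at 30 drops below 80% only when ρ is under about 0.07. At ρ = 0 the normal approximation gives n = 29.89, which rounds up to 30, so even then the planned size meets 80% by the same approximation that returns the 15. Also at ρ = 0, a one-sided 5% test has 86.3% at 30, while equivalence has 72.5% at 5% per side and 54.7% at 2.5% per side.

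**The case for a change.** The best case for asking for a change is that it would cost a few sentences and would settle three things: which test the 80% describes, what power the 30 subjects provide, and what kind of SD 0.069 is. At 15 subjects the candidate tests range from 49.1% to 84.7%, so the sentence as written cannot be tied to one of them. The SD question is the only one with any reach, since a single-eye SD with almost no between-eye correlation would bring power at 30 below 80% for the two-sided test, and an equivalence test would be hit harder.

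All of that is fair as a comment on completeness, and the calculations behind it are correct. It does not show an error. The stated figure reproduces from numbers in sections 7.2, 7.3 and 7.6, and planning a t test by normal approximation is common practice; here it moves the answer from 17 to 15 in a trial that enrols about 30. The unfavourable SD reading needs two eyes of the same person to be almost uncorrelated in acuity, and nothing in the documents suggests that. Section 7.3 also describes power as if it were the Type II error rate. That is a clerical slip: the same paragraph goes on to treat higher power as better, so no calculation is affected.

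**Conclusion.** The concern does not call for a change. The 15-subject figure is a minimum that reproduces by a standard approximation (14.95, power 80.1%). The 74.2% depends on inferring that two-sided route and then applying the exact t distribution; a one-sided 5% test of the stated margin gives 84.7%.

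The planned enrolment is twice that minimum. With 0.069 as the SD of the between-eye difference, δ = 0.05 and a true difference of 0 for the margin tests, power at 30 is 93.9% to 98.7%, and at least 87.0% with 25 completers. The one reservation is the type of SD. On the single-eye reading, two-sided power at 30 falls below 80% only for a correlation under about 0.07, although the equivalence tests would be less well protected at low correlation.

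Writing down the missing inputs and a power for 30 would make section 7.3 easier to read. It would alter neither the enrolment, nor the analysis, nor any result, and section 7.6.1 sets no pass/fail criterion that depends on the power figure. The documents leave a gap in reporting that a statistician can fill from sections 7.2, 7.3 and 7.6.

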7.4 Randomization

To minimize or avoid bias, subjects will be assigned randomization numbers as they are enrolled according to unique randomization schedules created for the study. The randomization schedule will be produced prior to study enrollment. Subjects will be receiving each of the study lens types once, in a randomized order. An effort will be made to conceal the CTM materials from the subject and the investigator throughout the study. Both the study subject and investigator will be masked.

7.5 Study Populations

Subjects will be included in all summaries under the treatment that they actually received. Analyses of safety data will include all dispensed subjects. All other summaries will include all eligible, completed subjects.

7.6 Statistical Analysis

Continuous data will be summarized using descriptive statistics: n, mean, standard deviation, median, minimum and maximum. Categorical data will be presented by the total counts for each category and corresponding percentages. The data for each of the ordinal dependent measures (i.e., those assigned a clinical grade) will be analyzed using appropriate nonparametric techniques. Unless otherwise noted, paired t tests will be used to test for

differences in means for each of the parametric dependent variables. Differences at the $p \leq 0.05$ level will be considered statistically significant.

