5.1 Study Visits

5.1.1 METHODOLOGY:

Visit 1, Insertion

- Subjects will have at least an 8 hour no lens washout period prior to their insertion visit.
- Limbal and bulbar redness, corneal and conjunctival staining will be assessed with the slit lamp.
- Percent area staining covered will be assessed for all 5 quadrants of the cornea.
- A baseline spherical refraction will be performed, through which High Contrast/High Illumination (HCHI) logMAR visual acuity will be measured at 6m.
- Each subject will insert a randomized lens pair.
- Evaluate: sting/burn, dryness, comfort after 3 minutes of lens wear, centration, movement, wettability, deposits and preference based on comfort.
- Spherical over-refraction will be performed through which HCHI logMAR visual acuity will be measured at 6m.
- The subject will be instructed to wear the lens pair for approximately 2 hours.

Visit 2, Follow-up After 2 Hours of Lens Wear

- Spherical over-refraction will be performed through which HCHI logMAR visual acuity will be measured at 6m.
- Evaluate: sting/burn, dryness, comfort, preference for comfort, centration, movement, wettability, deposits and preference based on comfort.
- Limbal and bulbar redness will be re-assessed.
- Lenses will be harvested, stored dry in a standard case.
- Corneal and conjunctival staining will be re-assessed with the slit lamp.

- Percent area staining covered will be assessed for all 5 quadrants of the cornea.
- Digital photos of the cornea, conjunctiva, and lenses in situ may be acquired.

Grading scales for the biomicroscopic evaluations and subject assessments are according to applicable Research Clinic procedures. See Appendix A: Methods of Clinical Evaluation.

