7.0 STATISTICAL METHODS

7.1 Study Endpoints

Primary Endpoint:

1. Normalized logMAR Visual Acuity

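### Section 7.2 sets a 0.05 logMAR margin, but Section 7.6 plans only a paired t test of mean differences, so the stated hypothesis has no matching analysis

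*Combined protocol and SAP*

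**What the plan says.** The trial is contralateral, "test lens in one eye and control lens in the other eye" (Section 3.1), with about 30 subjects. The primary endpoint in Section 7.1 is "Normalized logMAR Visual Acuity". No section defines the normalization or names the primary visit. In Section 7.2 the null hypothesis is that "the difference in mean normalized logMAR VA between the two lens types is 0.05 or greater", and the alternative is a difference below 0.05. Neither a direction nor an absolute value is given.

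Section 7.3 reports that in an earlier study "the standard deviation for logMAR VA was 0.069" and that 15 subjects give 80% power. It does not say which quantity has that SD, or whether the 5% error rate is one-sided or two-sided.

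For the analysis, Section 7.6 says "Unless otherwise noted, paired t tests will be used to test for" mean differences in the parametric variables, and the Synopsis has the same rule: "paired t tests will be used to test for differences in means for each of the parametric dependent variables". No confidence interval, margin comparison or covariate is mentioned for VA. Section 7.6.1 sets no pass/fail criteria, and 7.6.3 plans no sensitivity analysis.

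Before insertion at Visit 1, "A baseline spherical refraction will be performed, through which High Contrast/High Illumination (HCHI) logMAR visual acuity will be measured at 6m" (Section 5.1.1). With lenses in place at both visits, "Spherical over-refraction will be performed through which HCHI logMAR visual acuity will be measured at 6m". No analysis use is stated for the baseline value.

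**The concern.** A paired t test of zero difference and a test against a 0.05 margin answer different questions. Significance in the first shows that the lenses differ by something, possibly by less than the margin. Non-significance shows only that zero was not excluded, and it leaves the 7.2 null standing unless an interval also excludes 0.05. Section 7.3 adds to the mismatch: it describes power as the chance of detecting a difference that exists, whereas under 7.2 power is the chance of concluding that the difference is small.

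With no pass/fail rule, the primary estimate and its uncertainty carry the whole interpretation. As written, the report could give a p-value that does not bear on the stated hypothesis.

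A lesser matter is that baseline VA is collected and could sharpen the estimate, but has no stated role.

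**Working it through.** Differences are Test minus Control. Higher logMAR is worse, so a positive value means Test is worse.

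**Inputs.** Margin 0.05 (7.2); SD 0.069, n = 15 and power 80% (7.3); about 30 subjects (3.1). Assumed, because the documents do not give them: true difference 0, inter-eye correlation ρ, and correlation r between the baseline and primary-visit inter-eye differences.

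**The plan's own figure.** n = [SD × (z_α + z_power) / 0.05]².
- One-sided 0.025: [0.069 × (1.960 + 0.842) / 0.05]² = 14.95, so 15. This reproduces.
- One-sided 0.05: [0.069 × (1.645 + 0.842) / 0.05]² = 11.77, so 12. This does not.

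A two-sided 5% test to detect a difference of 0.05 also gives 14.95. The figure therefore cannot show which test was meant. It does show that 0.069 was used as the SD of the paired difference.

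**The test as written, n = 30.** The half-width of the 95% interval is 2.045 × SD / √30.
- SD 0.069: half-width 0.0258. An observed difference of 0.026 is significant, with an interval of about 0.000 to 0.052. An upper limit below 0.05 needs an observed difference below 0.05 − 0.0258 = 0.0242.
- SD 0.0976: half-width 0.0364. An upper limit below 0.05 needs an observed difference below 0.0136. Any observed difference from 0.0136 to 0.0364 is non-significant and yet leaves the 7.2 null unrejected. For example, 0.030 has an interval of −0.006 to 0.066.

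**Power when the interval is read against 0.05.** If 0.069 is a single-eye SD, the paired SD is 0.069 × √(2(1 − ρ)): 0.0976 at ρ = 0, 0.0845 at ρ = 0.25 and 0.069 at ρ = 0.5. For the upper-limit rule, unadjusted power comes from the noncentral t with 29 df and noncentrality 0.05 × √30 / SD (3.97 at SD 0.069, 2.81 at 0.0976). Adjusted power is simulated with 60,000 trials, using the regression intercept with 28 df.

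| Paired SD | Unadjusted | Adjusted, r = 0 / 0.3 / 0.5 / 0.7 |
|---|---|---|
| 0.069 | 97% | 96 / 98 / 99 / 99.9% |
| 0.085 | 88% | 87 / 90 / 94 / 99% |
| 0.098 | 77% | 76 / 80 / 87 / 96% |

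If both 95% limits must lie within ±0.05, simulated unadjusted power is about 94% at SD 0.069 and 55% at SD 0.098.

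**Effect of adjustment (upper-limit rule).** The adjusted-to-unadjusted variance ratio is (1 − r²)(1 + 1/27), which breaks even at r = 0.19. At paired SD 0.069 the gain is at most 3 points. At 0.098 it is 86.7 − 77.4 = 9 points at r = 0.5 and 96.1 − 77.4 = 19 at r = 0.7. The largest loss is 77.4 − 75.9 = 1.5 points, at r = 0.

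**If normalized means change from baseline.** Suppose 0.069 is the raw paired SD and the baseline and later variances are equal. The change-score SD is then 0.069 × √(2(1 − r)), and upper-limit power is 77 / 90 / 97 / 99.9% at r = 0 / 0.3 / 0.5 / 0.7. If 0.069 is itself the change-score SD, it is 97% throughout. The endpoint and the SD therefore have to be defined together.

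**Scoring text.** Appendix A 1.1 lets a subject start below the top line and converts total letters read, with the full top row equal to 0.30. Starting at the 0.00 line and reading 5 + 3 letters gives 0.40 − 0.02 × 8 = 0.24 if skipped lines earn nothing. It gives 0.40 − 0.02 × (15 + 8) = −0.06 if the three skipped lines are credited.

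**The case against.** The strongest reply is that a paired t test can be run against a null of 0.05, that 7.2 supplies this null value, and that such a test is equivalent to reading a confidence limit. That may be the intent. However, 7.6 uses one sentence for every parametric variable, describes testing for differences, and mentions neither a margin nor an interval. The reply also leaves open the direction and whether one limit or both must meet the margin.

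It is also fair that no decision depends on this, since 7.6.1 sets no pass/fail criteria, and that on the reading that reproduces n = 15, power at n = 30 is already 97%. Both points stand. They limit the consequence and make baseline adjustment a modest extra, but they do not give 7.2 a matching analysis.

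Four stronger readings are tempting and not supported:
- *That a lens shown to be within the margin would be declared worse.* At SD 0.069 the interval around 0.026 reaches 0.052, so only the point estimate is inside.
- *That VA is compared without any baseline correction.* The undefined normalization may already be one.
- *That omitting baseline biases the result.* Lenses are randomized between eyes, so the unadjusted paired test is valid and only precision is at issue.
- *That VA is mis-scored.* Steps 3 and 4 of Appendix A 1.1 require a full line before moving down, which suggests the lines above count as read. Step 5 records letters per line, and the listed acuity software may credit them. Equal skipping in both eyes would cancel in the paired difference.

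**Conclusion.** The mismatch between 7.2 and 7.6 is real and should be corrected. Its size depends on what 0.069 measures and on which hypothesis is meant. At n = 30 and no true difference, unadjusted power is about 97% (upper limit only) or 94% (both limits) if 0.069 is the paired-difference SD. It is about 77% or 55% if 0.069 is a single-eye SD with inter-eye correlation 0.

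Baseline adjustment is a secondary improvement in precision. The gains at paired SD 0.098 rest on assumed correlations of 0.5 to 0.7 that the documents do not give. The scoring text needs clarification only; no error is established there.

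**What to change.** 1. **Section 7.6:** report the mean Test-minus-Control difference in logMAR VA at the primary visit with a two-sided 95% confidence interval, and compare the interval with the 0.05 margin.
2. **Section 7.2:** state either one-sided non-inferiority (Test worse by less than 0.05, upper limit below 0.05) or two-sided equivalence (both limits within ±0.05).
3. **Section 7.1:** define the normalization and name the primary visit.
4. **Section 7.3:** state the sidedness of alpha and which quantity 0.069 is the SD of.
5. **Section 7.6, recommended:** obtain the interval by regressing each subject's primary-visit Test-minus-Control difference on the baseline Test-minus-Control difference, not mean-centred. The intercept is the lens effect. If normalization already corrects for baseline, reconcile the two.
6. **Appendix A 1.1, step 7:** say that every line above the highest line read is credited with 5 letters, or that the VA software does this.

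The cost is wording, with no added visits or procedures. Item 5 needs baseline VA for each eye, which the contralateral design implies but Section 5.1.1 does not write, so say so there. It also uses one degree of freedom, about 4% more variance if r = 0. If equivalence is chosen and 0.069 proves to be a single-eye SD, the statement on sample size would need to be revisited.
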